5.4 Study Treatment Discontinuation

Subjects may discontinue study treatment or withdraw their consent to participate in the study at any time without prejudice. The investigator may withdraw a subject from study treatment or from the study if, in his or her clinical judgment, it is in the best interest of the subject or if the subject cannot comply with the protocol.

In addition, any of the following conditions require discontinuation of the subject from study treatment:

- An AE or intercurrent illness that in the opinion of the investigator warrants the subject's withdrawal from study treatment;
- The investigator believes it is not in the best interest of the subject to continue on study
- Specific conditions described in the Management of Adverse Events Sections 8.2.4.1;
- Necessity for treatment with other anticancer treatment prohibited by protocol;
- Sexually active subjects who refuse to use medically accepted barrier methods of contraception (eg, male condom, female condom) during the course of the study and for 4 months after discontinuation of study treatment;
- Women who become pregnant or are breastfeeding;
- If the subject does not recover from his or her toxicities to tolerable Grade ≤ 2 within 6 weeks, the subject will have study treatment discontinued unless there is unequivocal evidence that the subject is benefitting. In this situation, a subject may be able to restart therapy with a dose reduction upon resolution of the toxicity and with agreement of the principal investigator / Sponsor;
- Request by regulatory agencies for termination of treatment of an individual subject or all subjects under the protocol;
- Significant noncompliance with the protocol schedule in the opinion of the investigator;
- Subjects who cannot tolerate the minimum protocol-specified dose of study treatment will have study treatment discontinued;
- Progressive disease (PD) or the subject no longer experiences clinical benefit as determined by the investigator

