- ii. Uncontrolled hypertension defined as sustained blood pressure (BP) > 150 mm Hg systolic or > 100 mm Hg diastolic despite optimal antihypertensive treatment.
 - iii. Stroke (including transient ischemic attack [TIA]), myocardial infarction (MI), or other ischemic event, or thromboembolic event (eg, deep venous thrombosis, pulmonary embolism) within 6 months before first dose.
 - b. Gastrointestinal (GI) disorders including those associated with a high risk of perforation or fistula formation:
 - i. The subject has evidence of tumor invading the GI tract, active peptic ulcer disease, inflammatory bowel disease (eg, Crohn's disease), diverticulitis, cholecystitis, symptomatic cholangitis or appendicitis, acute pancreatitis, acute obstruction of the pancreatic duct or common bile duct, or gastric outlet obstruction.
 - ii. Abdominal fistula, GI perforation, bowel obstruction, or intra-abdominal abscess within 6 months before first dose.
Note: Complete healing of an intra-abdominal abscess must be confirmed before first dose.
 - c. Clinically significant hematuria, hematemesis, or hemoptysis of > 0.5 teaspoon (2.5 ml) of red blood, or other history of significant bleeding (eg, pulmonary hemorrhage) within 12 weeks before first dose.
 - d. Cavitating pulmonary lesion(s) or known endotracheal or endobronchial disease manifestation.
 - e. Lesions invading or encasing any major blood vessels.
 - f. Other clinically significant disorders that would preclude safe study participation.
 - i. Serious non-healing wound/ulcer/bone fracture.
 - ii. Uncompensated/symptomatic hypothyroidism.
 - iii. Moderate to severe hepatic impairment (Child-Pugh B or C).
10. Major surgery (eg, GI surgery, removal or biopsy of brain metastasis) within 8 weeks before first dose of study treatment. Complete wound healing from major surgery must have occurred 1 month before first dose and from minor surgery (eg, simple excision, tooth extraction) at least 10 days before first dose. Subjects with clinically relevant ongoing complications from prior surgery are not eligible.
11. Corrected QT interval calculated by the Fridericia formula (QTcF) > 500 ms per electrocardiogram (ECG) within 28 days before first dose of study treatment [32].

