8.2.4.1 Cabozantinib Adverse Events

The most frequent AEs experienced by $\geq 20\%$ of subjects treated with cabozantinib in descending order of frequency were diarrhea, fatigue, decreased appetite, nausea, weight decreased, PPES, vomiting, constipation, hypertension, dysgeusia, dysphonia, asthenia, and dyspnea. For a full description of the safety profile of cabozantinib, refer to the Cabozantinib Investigator's Brochure.

Other medically important but less frequent AEs including arterial thrombotic AEs (eg, transient ischemic attack [TIA], and myocardial infarction [MI]) and venous thrombotic AEs (eg, deep vein thrombosis [DVT] and pulmonary embolism), severe hemorrhagic events, proteinuria, wound healing complications, gastrointestinal (GI) perforation, abscesses including intra-abdominal and pelvic abscess, GI and non-GI fistula formation, osteonecrosis, and reversible posterior leukoencephalopathy syndrome (RPLS).

Adverse events associated with laboratory abnormalities experienced by $\geq 5\%$ of subjects treated with cabozantinib in descending order of frequency were anemia, AST increased, ALT increased, hypothyroidism, hypokalemia, hypomagnesemia, thrombocytopenia, hypocalcemia, hypophosphatemia, lactate dehydrogenase (LDH) increased, lipase increased, neutropenia, hyponatremia, ALP increased, leukopenia, and hyperglycemia.

Adverse events may occur within the first few weeks in the course of treatment with cabozantinib, as cabozantinib is expected to reach steady state exposure at approximately 2 weeks following first dose. Events that generally have an early onset include hypocalcemia, hypokalemia, thrombocytopenia, hypertension, PPES, abdominal pain, mucosal inflammation, constipation, diarrhea, and vomiting. Adverse events should be managed with supportive care at the earliest signs of toxicity. Dose reductions and treatment interruptions should be considered. Dose reductions are recommended for events that, if persistent, could become serious or intolerable (Section 8.2.2).

Cabozantinib should be discontinued for the following AEs: visceral perforation or fistula formation, severe hemorrhage, serious arterial thromboembolic events, nephrotic syndrome, hypertensive emergency, persistent uncontrolled hypertension despite optimal medical management, and RPLS.

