8.2.4.1.3 Hemorrhage

Hemorrhagic events, including serious and sometimes fatal events, have been reported with cabozantinib. Subjects should be monitored for bleeding events with serial complete blood counts and physical examination while on study.

Risk factors for hemorrhagic events may include (but may not be limited to) the following:

- Tumor of the lung with cavitory lesions or tumor lesions which invade or encase major blood vessels. NSCLC with squamous cell differentiation is known for significant lung cavitations and centrally located tumors that may invade major blood vessels. Thus, the anatomic location and characteristics of tumor as well as the medical history should be carefully reviewed in the selection of subjects for treatment with cabozantinib.
- Recent or concurrent radiation to the thoracic cavity.
- Active peptic ulcer disease, inflammatory GI diseases including Crohn's disease and ulcerative colitis.
- Underlying medical conditions which affect normal hemostasis (eg, deficiencies in clotting factors and/or platelet function, or thrombocytopenia).
- Concomitant medication with anticoagulants or other drugs which affect normal hemostasis.
- History of clinically significant hemoptysis, hematemesis, or hematuria.

The risk of hemorrhage in cabozantinib-treated subjects with brain metastases has not been thoroughly analyzed. Though the incidence of CNS hemorrhage events in a study of subjects with glioblastoma was higher than observed in general population of subjects with cancer treated with cabozantinib, it is not clear how the risk of hemorrhage in glioblastoma translates to a risk of hemorrhage for subjects with brain metastases. Currently, brain metastases of carcinomas are not contraindications to the use of cabozantinib, but subjects with brain metastases should be monitored with a high index of suspicion if symptoms that could be due to a CNS hemorrhage occur.

Complete healing from radiation-induced side effects should have occurred before initiating cabozantinib treatment, and cabozantinib should be discontinued in subjects with serious and life-threatening bleeding events or recent hemoptysis (≥ 2.5 mL of red blood).

Cabozantinib should be discontinued in subjects with serious and life-threatening bleeding events or recent hemoptysis (≥ 2.5 mL of red blood).

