8.2.4.1.5 Hypertension

Table 8-5 provides treatment guidelines for hypertension deemed related to cabozantinib. Blood pressure should be monitored in a constant position visit to visit, either sitting or supine in a relaxed setting. Decisions to reduce or interrupt the dose of study treatment must be based on BP readings taken by a medical professional and must be confirmed with a second measurement at least 5 minutes following the first measurement.

Cabozantinib should be discontinued in subjects with hypertensive emergency.

Table 8-5: Management of Hypertension Associated with Cabozantinib

Criteria for Dose Modifications	Treatment/Cabozantinib Dose Modification
Subjects NOT receiving optimized anti-hypertensive therapy	
> 150 mm Hg (systolic) ^a and < 160 mm Hg OR > 100 mm Hg (diastolic) and < 110 mm Hg	
 Optimize antihypertensive medications by adding new or additional antihypertensive medications and/or increase dose of existing medications. Reduce cabozantinib treatment by one dose level if optimal antihypertensive therapy (usually to include 3 agents) does not result in BP <150 mm Hg systolic or <100 mm Hg diastolic If subject is symptomatic interrupt cabozantinib treatment
≥ 160 mm Hg (systolic) OR ≥ 110 mm Hg (diastolic)	
 Reduce cabozantinib by one dose level^b or interrupt cabozantinib treatment per investigator discretion Add new or additional anti-hypertensive medications and/or increase dose of existing medications and monitor subject closely for hypotension. If optimized antihypertensive therapy (usually to include 3 agents) does not result in BP < 150 mm Hg systolic or < 100 mm Hg diastolic, cabozantinib treatment should be dose reduced further or interrupted Cabozantinib treatment should be dose interrupted if upper limits of systolic BP (≥ 160 mm Hg) are sustained and not adequately manageable or if systolic BP is > 180 mm Hg or diastolic BP > 110 mm Hg, or if subject is symptomatic Re-start cabozantinib treatment at the most tolerable dose and re-escalate only if BP falls to and is sustained at < 150 mm Hg systolic and < 100 mm Hg diastolic
Hypertensive emergency ^c	
 Discontinue cabozantinib treatment

BP, blood pressure.

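### Section 8.2.4.1 discontinues cabozantinib for hypertension that persists on optimal management; Table 8-5 only reduces or interrupts it when optimal therapy fails, and the two are not reconciled

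*Combined protocol and SAP*

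**What the plan says.** Section 8.2.4.1 closes with a list of stopping events. It opens "Cabozantinib should be discontinued for the following AEs: visceral perforation or fistula formation, severe hemorrhage" and ends "nephrotic syndrome, hypertensive emergency, persistent uncontrolled hypertension despite optimal medical management, and RPLS". Two of its items concern blood pressure, and they are separate: hypertensive emergency, and hypertension that stays uncontrolled on optimal management.

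Section 5.4 says that "any of the following conditions require discontinuation of the subject from study treatment", and one entry in what follows is "Specific conditions described in the Management of Adverse Events Sections 8.2.4.1".

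Table 8-5, in Section 8.2.4.1.5, gives the detailed rules for hypertension related to cabozantinib:

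- Lower band (systolic above 150 and below 160, or diastolic above 100 and below 110 mm Hg): "Reduce cabozantinib treatment by one dose level if optimal antihypertensive therapy (usually to include 3 agents) does not result in BP" under 150 systolic or 100 diastolic.
- Higher band (systolic 160 or more, or diastolic 110 or more): if optimized therapy fails against the same limits, the dose is reduced further or the drug is interrupted.
- Also in the higher band: "Cabozantinib treatment should be dose interrupted if upper limits of systolic BP (≥ 160 mm Hg) are sustained and not adequately manageable". A re-start bullet follows, in which re-escalation requires BP to fall and stay below 150 and 100.
- Hypertensive emergency: discontinue.

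The table and the text above it contain no other discontinuation trigger.

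**The concern.** Both places address blood pressure that optimal antihypertensive treatment has not controlled. One ends cabozantinib; the other keeps the subject on a reduced dose or on hold, with a route back to dosing. An investigator reading the list and an investigator reading the table can both follow the protocol and do opposite things with the same subject.

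Two things are at stake. The first is consistent safety management across sites. The second is the secondary tolerability endpoint in Section 4.0, the rate of discontinuation of study drug(s) due to adverse events. A subject handled under the list counts as an event; the same subject handled under the table does not, unless some other rule later ends treatment. The reported rate would then partly reflect which part of Section 8 a site consulted.

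**Working it through.** The plan states no figure on this point, so the check is mainly a comparison of text.

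**Step 1. The two places side by side.**

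| State | Section 8.2.4.1 list | Section 8.2.4.1.5 and Table 8-5 |
|---|---|---|
| Hypertensive emergency | Discontinue | Discontinue |
| BP not brought below the limits by optimal therapy, lower band | Discontinue, if this counts as persistent and uncontrolled | Reduce one dose level |
| BP not brought below the limits by optimized therapy, higher band | Discontinue, on the same condition | Reduce further or interrupt |
| Systolic 160 or more, sustained and not adequately manageable | Discontinue, on the same condition | Interrupt; re-start bullet follows |

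They agree on emergency and differ on the other three rows. The condition in the middle column cannot be tested, because no section defines *persistent* or says how long BP must stay raised on optimal treatment.

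**Step 2. Is this item treated like the others in the list?** The list has seven items. Six have a stop instruction in their own subsection: perforation or fistula (8.2.4.1.1 and 8.2.4.1.2), hemorrhage (8.2.4.1.3), arterial events (8.2.4.1.4), hypertensive emergency (8.2.4.1.5), nephrotic syndrome (8.2.4.1.9) and RPLS (8.2.4.1.10). Persistent uncontrolled hypertension is the only one without.

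**Step 3. Do the general rules settle it?**

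- The dose-modification bullets before Table 8-2 discontinue cabozantinib after more than 6 weeks of interruption for related events, except where benefit is unequivocal. The list in 8.2.4.1 has no such exception, and the rule does not reach a subject who is reduced rather than interrupted.
- The note to Table 8-2 discontinues cabozantinib if 20 mg is not tolerated. It acts only once the subject is at 20 mg, and the documents do not say whether uncontrolled BP at that dose counts as intolerance.

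Neither rule reproduces the stop in the list.

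**Step 4. Size.** Section 11 allows up to 27 subjects, of whom 23 are needed for the primary analysis. The denominator of the tolerability rate is not stated, so both are shown:

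- one subject reclassified: 1/27 = 3.7 percentage points; 1/23 = 4.3 percentage points.

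For context, Table 3-3 reports hypertension in 3/18 (17%) on the triplet, all Grade 3-4. At that frequency, 27 × 3/18 = 4.5 subjects would have hypertension. How many of them would be refractory to optimal therapy is not given anywhere.

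**The case against.** The strongest reply is that the two places form a ladder. The paragraph just before the stop list in 8.2.4.1 says reductions and interruptions should be considered, and recommends reductions for events that could become serious if they persist. On that view Table 8-5 gives the intermediate steps, and the list gives the end point when those steps fail. This reading is reasonable, and it makes the defect an ambiguity rather than an unavoidable contradiction. But the sequence is written nowhere, the end point is undefined, and the table's last step short of emergency is interruption with a re-start bullet.

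It can also be said that Section 5.4 does not rank the list above the table, since Table 8-5 itself sits within 8.2.4.1. That is correct, and it means 5.4 cannot be used to decide between them.

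Several stronger readings are tempting and are not supported:

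- **That the stop is expressly permanent.** Section 8.2.4.1 says only that the drug should be discontinued, although the protocol does separate that from interruption.
- **That Table 8-5 restarts the drug while BP is still uncontrolled.** The BP condition governs re-escalation and arguably the restart too, and Section 8.2.3 ties restart after a possibly related toxicity to recovery to Grade 1 or baseline.
- **That subjects already on optimized therapy have no row.** The heading suggests so, but the bullets beneath it say what to do when optimized therapy fails.
- **That exclusion 9a supplies the missing definition.** It reads "Uncontrolled hypertension defined as sustained blood pressure (BP) > 150 mm Hg systolic or > 100 mm Hg diastolic despite optimal antihypertensive treatment", with the same numerical limits, but it is a screening criterion and nothing extends it to on-treatment management.
- **That the hemorrhage stop shows the same conflict.** Section 8.2.4.1.3 says "cabozantinib should be discontinued in subjects with serious and life-threatening bleeding events or recent hemoptysis", while the list says severe hemorrhage. The wording differs, but both places discontinue. Reading *severe* as Grade 3-4 would borrow from a background sentence on ipilimumab.

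**Conclusion.** The inconsistency stands as a drafting conflict. For BP uncontrolled despite optimal therapy, Section 8.2.4.1 discontinues cabozantinib and Table 8-5 reduces or interrupts it; the documents give neither a sequence nor a definition that would reconcile them.

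The effect on the endpoint is about 4 percentage points per reclassified subject, assuming a denominator of 27 (or 23) and a subject not already counted for another event. A reader might go further and project a discontinuation rate from the phase 1 frequency of hypertension. The documents do not support that: they give no rate of failure of optimal therapy, and according to Section 3.5 both discontinuations among the 18 phase 1 subjects were for colitis and hepatitis, none for hypertension.

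The affected endpoint is secondary, Section 11 treats the analyses other than PFS and OS as descriptive, and the test of 1-year PFS is not directly affected. The point should be fixed because it concerns safety instructions, not because it threatens the main conclusion.

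**What to change.** Reconcile Section 8.2.4.1 with Section 8.2.4.1.5 and Table 8-5:

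1. State one disposition, or one explicit sequence of steps, for BP that stays uncontrolled despite optimal therapy, and use it in both places.
2. Define *persistent uncontrolled* for on-treatment use.
3. Cross-refer the stop list and Table 8-5.
4. Align the table's heading, which names subjects not on optimized therapy, with the bullets that deal with failed optimized therapy.

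Which rule stands is for the sponsor to decide; this review takes no position on it. The cost is amendment wording only, with no change to sample size, assessments or analysis.

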8.2.4.1.1 Gastrointestinal Disorders

Gastrointestinal perforation, GI fistula, and intra-abdominal and pelvic abscess: After starting treatment with cabozantinib, subjects should be monitored for early signs of GI perforation such as abdominal pain, nausea, emesis, constipation, and fever especially if known risk factors for developing GI perforation or fistula (Turnage and Badgwell 2016) are present. Discontinue cabozantinib and initiate appropriate management in subjects who have been diagnosed with GI perforation or fistula.

Diarrhea: Subjects should be instructed to notify their physician immediately at the first signs of poorly formed or loose stool or an increased frequency of bowel movements. Guidelines for the evaluation and management of diarrhea are shown in Table 8-4. Patients and treating providers need to be aware that diarrhea may occur as a non-immune mediated event with cabozantinib or as an immune mediated event with nivolumab/ipilimumab. Directions outlined here refer to non-immune mediated diarrhea. Administration of antidiarrheal/antimotility agents is recommended at the first sign of diarrhea as initial management. Some subjects may require concomitant treatment with more than one antidiarrheal agent. When therapy with antidiarrheal agents does not control the diarrhea to tolerable levels, cabozantinib should be temporarily interrupted or dose reduced. When the diarrhea is controlled, retreatment with cabozantinib may be acceptable per investigator decision. In addition, general supportive measures should be implemented such as continuous oral isotonic hydration, correction of fluid and electrolyte abnormalities, small frequent meals, and stopping lactose-containing products, high-fat meals, and alcohol.

Recurrent or prolonged diarrhea can be associated with anal or perianal skin erosions which increase the risk for anal abscesses, fistulas, or proctitis. Good personal hygiene should be emphasized. Regular examinations of the perianal region should be performed whenever diarrhea has occurred during treatment with cabozantinib. Infections of the perianal region should be treated per local guidelines.

Table 8-4: Management of Diarrhea Associated with Cabozantinib

Status	Management
Tolerable Grade 1-2 (duration < 48 h)	
 • Continue with study treatment and consider dose reduction • Initiate treatment with an antidiarrheal agent (eg, loperamide 4 mg followed by 2 mg after each episode of diarrhea [maximum: 16 mg loperamide per day]) • Dietary modifications (eg, small lactose-free meals, bananas and rice) • Intake of isotonic fluids (1-1.5 L/day) • Re-assess after 24 hours: 
 ○ Diarrhea resolving to baseline bowel habits: gradually add solid foods and discontinue or decrease antidiarrheal treatment after 12 h diarrhea-free interval ○ Diarrhea not resolving: Continue/resume antidiarrheal treatment
Intolerable Grade 2, Grade 2 > 48 h, or ≥ Grade 3	
 • Interrupt study treatment • Ask subject to attend clinic • Rule out infection (eg, stool sample for culture) 
 ○ Administer antibiotics as needed (eg, if fever or Grade 3-4 neutropenia persists > 24 h) • Administer fluids (1-1.5 L/day orally or IV, as appropriate) for hydration or to correct electrolyte abnormalities • For Grade 3-4 or complicated lower grade diarrhea consider hospitalization and IV hydration • Re-assess after 24 h 
 ○ Diarrhea resolving to baseline bowel habits or Grade ≤ 1: consider restarting study treatment at reduced dose ○ Diarrhea not resolving: Start and or continue antidiarrheal treatment (eg, loperamide 4 mg followed by 2 mg after each episode of diarrhea [maximum: 16 mg loperamide per day]). Consider starting second line antidiarrheal or referral to gastroenterologist

Nausea and vomiting: Antiemetic agents are recommended as clinically appropriate for treatment or prophylaxis of nausea and vomiting, along with supportive care. Dehydration and electrolyte abnormalities may be associated with vomiting and monitoring for and correction of fluid and electrolyte disturbances should be implemented. Antiemetic medications should be assessed for potential drug interactions (refer to Section 9.3 for further details).

